5.2 Treatment Period

During the Treatment Period, subjects will receive pembrolizumab and oxaliplatin on Day 1 and capecitabine on Days 1-14 of each 21-day cycle until either: 1) disease progression; 2) the occurrence of unacceptable treatment-related toxicity; or 3) other reason(s) for subject discontinuation as described in [Section 5.7](#). Toxicity-related dose modifications of pembrolizumab, capecitabine and oxaliplatin may occur during the Treatment Period. Dose modification guidelines are described in [Section 7.1](#).

NOTE: For the dose expansion cohort only, the first cycle (i.e. biomarker cycle) will be modified to allow assessment of biomarkers related to pembrolizumab; the length will be 28 days. Patients will receive pembrolizumab monotherapy on Cycle 1 Day 1. Treatment with oxaliplatin and capecitabine will begin on Cycle 1 Day 8; capecitabine will be dosed for 14 days (ie. Days 8-21), followed by one week off drug (ie. Days 22-28). Cycle 2 will start on Day 29 of study (ie. 28 days after pembrolizumab monotherapy and 20 days after start of capecitabine and oxaliplatin). For cycles 2 and beyond, the cycle length is 21 days. A treatment window of +/- 3 days is allowed for day 1 of cycle 2 and all subsequent cycles.

All subjects will have study procedures weekly during the first cycle, then Day 1 of each cycle. After the completion of the first cycle, laboratory assessments may be obtained up to 3 days prior to treatment. If necessary, the treatment visit may be within +/- 3 days of the scheduled day 1 for cycle 2 and all subsequent cycles. If clinically indicated, additional visits and/or safety assessments may be warranted.

The following study procedures must be completed on **Day 1 of each cycle**:

- Physical examination
- Vital signs and weight
- Concomitant medications
- ECOG performance status
- Adverse event assessment
- CBC with differential
- Chemistries including LFTs

The following study procedures must be completed on **weekly in Cycle 1 only**:

- Physical examination
- Vital signs and weight
- Concomitant medications
- ECOG performance status
- Adverse event assessment
- CBC with differential
- Chemistries including LFTs

For **dose expansion cohort only**, the following study procedures must be completed **pre-dose on Cycle 1 Day 8**:

- PBMC
- Plasma
- Tumor biopsy (Can be performed on Day 7 if needed. Only applicable to patients in dose expansion that have lesions amenable to safe biopsy)

For **dose expansion cohort only**, the following study procedures must be completed **pre-dose on Cycle 1 Day 29 (i.e. Cycle 2 Day 1)**:

- PBMC
- Plasma

The following study procedures must be completed **every 3 (\pm 1) cycles**:

- Thyroid function tests
- Serum pregnancy test (only for women of childbearing potential)
- Tumor assessment (CT and/or MRI scans)
- Blood tumor marker, if clinically indicated (e.g., CEA or CA19-9)
- PBMC - first restaging only
- Plasma

Restaging scans will be performed every 3 cycles (ie. every 9 weeks) and disease response will be assessed using guidelines described in [Section 5.6](#).

The Treatment Period ends when a subject receives his or her last dose of study treatment; the subject then enters the Follow-up Period.

5.3 Follow-up Period

Subjects should return 30 (\pm 7) days after their last dose of study drug for an off-treatment visit to complete the following study procedures:

- Physical examination
- Vital signs and weight
- Concomitant medications
- ECOG performance status
- Adverse event assessment
- CBC with differential
- Chemistries including LFTs
- Thyroid function tests
- Serum pregnancy test (only for women of childbearing potential)
- Plasma
- Archived tissue collected at end of study (if available)

Additional follow-up may occur for subjects with adverse events (AEs) related to study drug that are ongoing at the time of this off-treatment visit unless AE is deemed unresolvable or subject has started a new anti-cancer treatment regimen.

For subjects that are discontinued from study treatment for reasons other than disease progression, subjects will have disease status (blood tumor marker(s) and restaging scans per standard of care schedule) followed until disease progression or start of new anti-cancer treatment regimen. Disease status may be collected by personal interviews or review of medical records. Disease progression follow up will continue for as long as patient is in survival follow up, provided they have not progressed or started a new anti-cancer treatment. For subjects that completed therapy and remain in complete response, PBMCs and plasma will be collected approximately every three months with standard of care visits, provided subjects consent to this additional follow-up.

Subjects will be followed for survival up to 3 years after the last subject starts the study drug regimen or until the study is closed (whichever comes first). Survival status may be collected by phone call or review of medical or public records approximately every 12 weeks.

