Subjects who discontinue study treatment for any reason (e.g., toxicity) other than disease progression should be followed until documented disease progression or start of a new anti-cancer therapy. All subjects will be followed for survival until death, loss to follow-up, or study completion.

Study completion is 3 years after the last subject starts study drug regimen.

Study Drug Regimen

In the Safety Validation Cohort, the cycle length is 21 days. Patients will receive pembrolizumab and oxaliplatin on day 1 of each cycle. Capecitabine will be taken twice per day on days 1-14 of each cycle. Patients will continue to receive study treatment until they experience unacceptable drug-related toxicity or disease progression.

In the Dose Expansion Cohort (ie. phase II), the first cycle of treatment, referred to as 'biomarker cycle,' will be modified to allow assessment of biomarkers related to pembrolizumab; the length will be 28 days. Patients will receive pembrolizumab monotherapy on Cycle 1 Day 1. Treatment with oxaliplatin and capecitabine will begin on Cycle 1 Day 8; capecitabine will be dosed for 14 days (ie. Days 8-21), followed by one week off drug (ie. Days 22-28). Cycle 2 will start on Day 29 of study (ie. 28 days after pembrolizumab monotherapy and 20 days after start of capecitabine and oxaliplatin). For cycles 2 and beyond, the cycle length is 21 days, with a treatment window of +/-3 days allowed for day 1. Patients will receive pembrolizumab and oxaliplatin on day 1 of each cycle. Capecitabine will be taken twice per day on days 1-14 of each cycle. Patients will continue to receive study treatment until they experience unacceptable drug-related toxicity or disease progression.

For both cohorts, patients will continue to receive study treatment until they experience unacceptable drug-related toxicity or disease progression. The maximum duration of treatment for pembrolizumab will be up to two years (35 cycles). The duration of treatment for capecitabine and oxaliplatin will be until unacceptable drug-related toxicity or disease progression. Patients who complete 35 cycles of therapy and have complete response or prolonged stable disease may also elect to end therapy with capecitabine, after a discussion with their treating physician.

Study Assessments

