9.1.1 Primary Endpoint

The primary endpoint will be progression-free survival (PFS) measured from study entry until documented progression or death from any cause. Patients who have not experienced progression will be censored at the date of the last radiographic assessment. Based on the results of the AVAGAST and ToGA trials a median PFS of approximately 5.5 months is expected for patients treated with oxaliplatin and capecitabine alone. Also, observed PFS hazard ratios of 0.80 and 0.71 were reported for AVAGAST and ToGA, respectively. With 35 patients enrolled, the difference between a historical median PFS of 5.5 months and experimental median of 7.3 months, a hazard ratio of 0.75, can be detected with 80% power (1-sided test of single exponential mean, $\alpha=0.2$).

PFS and median PFS will be estimated using the Kaplan-Meier method. The 95% confidence interval estimate for median PFS will be computed using the variance estimate proposed by Brookmeyer and Crowley. Under the alternative hypothesis, 32 PFS events are expected at the end of the follow-up period.

The primary analysis of PFS will be intention-to-treat in that all patients who have undergone at least one scheduled restaging on-treatment, or who have had unequivocal progression prior to the first scheduled restaging will be followed for progression. These patients will be followed for PFS, even if they are removed from treatment due to unacceptable toxicity or because they withdrew consent. As a secondary analysis, these patients will be censored at the time they were removed from treatment.

The magnitude of reduction in tumor burden will be summarized descriptively (such as a waterfall plot) based on change in the sum of the longest diameters of target lesions relative to baseline.

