23. Subjects discontinued from study treatment with no documented disease progression and no subsequent anti-cancer treatment should have disease status and blood tumor markers (if clinically indicated) followed per standard of care schedule until disease progression or start of new anti-cancer treatment regimen is documented. Disease status may be collected by personal interviews or review of medical records.
24. Subjects are followed for survival up to 3 years after the last subject starts the study drug regimen or until the study is closed (whichever comes first). Survival status may be collected by personal interviews or review of medical or public records.
25. Treatment visits may occur within +/-3 days of D1 for C2 and all subsequent cycles.
26. Cycle 1 day 1 only. After that, will redo at restaging visits.
27. Only for subjects who achieved a complete response and have consented to the additional collection.

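### Disease follow-up stops at new anti-cancer therapy while deaths still count as PFS events, and Section 9.1.1 has no rule for patients who switch before progression

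*Combined protocol and SAP*

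**What the plan says.** **Disease follow-up.** Section 5.3 follows patients who stop treatment for reasons other than progression "followed until disease progression or start of new anti-cancer treatment regimen". It adds that progression follow-up runs alongside survival follow-up "provided they have not progressed or started a new anti-cancer treatment". The synopsis (Estimated Length of Study Participation) has such patients "followed until documented disease progression or start of a new anti-cancer therapy", and Appendix D footnote 23 has the same limit: "until disease progression or start of new anti-cancer treatment regimen is documented".

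**Survival follow-up.** This has no such limit. The synopsis says "All subjects will be followed for survival until death, loss to follow-up, or study completion". Section 5.3 sets contacts about every 12 weeks, for up to 3 years after the last subject starts or until the study closes. The contact may be a phone call or a review of medical or public records.

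**Primary endpoint.** Section 9.1.1 defines PFS as "measured from study entry until documented progression or death from any cause". Its censoring rule is "Patients who have not experienced progression will be censored at the date of the last radiographic assessment". It describes the analysis as intention-to-treat and says of patients who leave treatment: "These patients will be followed for PFS, even if they are removed from treatment due to unacceptable toxicity or because they withdrew consent". A secondary analysis censors those patients when they are removed from treatment. New anti-cancer therapy is not mentioned in 9.1.1.

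**The concern.** A patient can leave study treatment without progression in several ways. Permanent discontinuation of pembrolizumab ends study treatment (Section 7.1), some toxicity rows end protocol therapy (7.1.2), and a need for other anti-cancer treatment is a listed reason to stop (5.7). In first-line metastatic disease some of these patients will start another regimen before progression is documented.

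From then on the study stops collecting progression but continues to collect death. If death is the next thing recorded and is taken as the PFS event, survival after the unobserved progression is added to PFS. That error can only lengthen PFS, and the trial has no concurrent control to share it: the sample-size argument sets 35 patients against a historical median of 5.5 months. If analysts instead censor at the last scan, the result differs, and nothing in 9.1.1 says which treatment of these patients is intended.

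**Working it through.** **1. One patient, three answers.** Suppose a patient stops for toxicity at month 3, starts a new regimen at month 4, progresses at month 7 and dies at month 14.

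| Treatment of the patient | PFS record |
|---|---|
| True value | event at 7 months |
| Death from any cause is the event | event at 14 months |
| No documented progression, so censored | censored at the last scan, no later than about month 4 |
| Secondary analysis | censored at 3 months |

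The month-7 progression is not collected under Section 5.3, so the true value cannot be recovered.

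**2. The plan's own figure.** Inputs from 9.1.1: n = 35, medians 5.5 and 7.3 months, hazard ratio 0.75, one-sided alpha 0.20, test of a single exponential mean. Reject if 2 × λ0 × (total time) exceeds the 80th percentile of chi-square with 2d degrees of freedom, where λ0 = ln 2 / 5.5 and d is the number of events. Power = P(chi-square with 2d df > critical value × HR). With d = 35 this gives 80.3% at HR 0.75 and 79.6% at 5.5 versus 7.3. The stated 80% reproduces and does not depend on this point.

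**3. Why a few patients matter to that test.** With d = 35 the critical value is 79.71 (70 df). The test is positive when mean time exceeds 79.71 / (2 × 0.1260 × 35) = 9.04 months. Under no benefit the mean is 5.5 / 0.693 = 7.93 months, so the margin is 1.11 months. Assume a 5-month median from progression to death, a mean of 5 / 0.693 = 7.2 months. If 10% of patients are scored at death, the overall mean rises by 0.10 × 7.2 = 0.72 month, about two-thirds of the margin. This ignores the end of follow-up, which the simulation includes.

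**4. Simulation.** Assumptions: n = 35, exponential PFS with true median 5.5 months (no benefit), 12-month accrual, 36 months of follow-up after the last entry, exponential time from progression to death. Switching is a competing exponential, unrelated to imminent progression. Switchers alive at the end are censored at the switch.

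| Switching before progression | Median, progression to death | One-sided error, switchers scored at death | Rise in mean Kaplan-Meier median |
|---|---|---|---|
| 10% | 3 / 5 / 8 months | 0.27 / 0.32 / 0.36 | about 0.2-0.25 month |
| 20% | 3 / 5 / 8 months | 0.36 / 0.46 / 0.54 | about 0.4-0.6 month |

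The lowest entry varied between 0.27 and 0.29 across runs. Censoring the same switchers at the switch leaves the error at about 0.20-0.21.

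**5. If switching is informative.** Place the switch uniformly before true progression and let the median from progression to death be 4-8 months. Death scoring then gives an error of 0.33-0.42 at 10% switching and 0.48-0.66 at 20%. Censoring gives about 0.30 and 0.43-0.44. Censoring is therefore neutral only when the switch carries no information about progression.

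**The case against.** **A reader might infer that the plan scores every switcher at death and so overstates PFS.** The documents do not settle this. Analysts would hold no progression record for such a patient, so the sentence "Patients who have not experienced progression will be censored at the date of the last radiographic assessment" can be read to censor at the last scan. That reading has its own difficulty: applied literally, it would censor every death without documented progression, against the definition that counts death from any cause. Death scoring is therefore the more natural reading, but not the only one. Switchers alive at the end are censored on either reading, and only those who progress unobserved before death have PFS lengthened.

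**A reader might also infer a flat contradiction between 5.3 and 9.1.1.** Section 9.1.1 promises PFS follow-up after removal from treatment, and 5.3 provides it up to new therapy. Neither says it continues beyond that. This is a missing rule that strains the intention-to-treat label rather than two incompatible instructions.

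**The secondary analysis is a partial check.** It would censor the example patient at month 3 and could expose some inflation. It applies to the removals 9.1.1 names, toxicity and withdrawn consent, and leaves the primary estimate unchanged.

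**The error rate is not tied to a decision.** The primary objective is to describe PFS, the reported analysis is a Kaplan-Meier median with a 95% interval, and the exponential test appears only in the sample-size statement. This stands. On the reported median, a shift of 0.2-0.25 month at 10% switching is under one-fifth of its sampling standard deviation of about 1.3 months. Unlike sampling error, it has a known direction.

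**Conclusion.** The gap is real and lies in the primary endpoint: the stop rule, continued survival follow-up and an unrestricted death event leave PFS undefined for a patient who switches before documented progression. On the ordinary reading, those who progress unobserved and die within follow-up get a PFS that is too long.

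The size rests wholly on assumptions, because the documents give neither a switching rate nor survival after progression. With 10-20% switching (3.5 to 7 of 35 patients) and a median of 3-8 months from progression to death, death scoring adds about 0.2-0.6 month to the median. The gain the trial is sized to detect is 7.3 − 5.5 = 1.8 months. The sample-size test's error rises from 0.20 to between about 0.3 and 0.54; under uninformative censoring it stays near 0.20. The choice of rule therefore matters, and it should be fixed before the data are analysed.

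**What to change.** **Follow-up text.** In Section 5.3, the synopsis and Appendix D footnote 23, stop using the start of new therapy as the end of disease follow-up. Keep recording the first progression date from routine-care records until progression, death or the end of survival follow-up. This matches the promise in 9.1.1 to follow these patients for PFS.

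**Analysis text.** In 9.1.1 state that a death after new therapy counts as a PFS event only if disease status was still being followed; otherwise censor at the last adequate scan before the new therapy. Report censoring at new therapy for all switchers as a sensitivity analysis, and give the number of switchers, since the censoring may be informative.

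**Separate, minor clarification.** The wording on withdrawn consent should distinguish withdrawal from treatment from withdrawal from follow-up.

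**Cost.** No study scans are added. Some extra record review is needed, because the 12-weekly survival contact may be only a phone call or a public record and would not show a scan result. The PFS estimate may be slightly less favourable.

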5.4 Laboratory Assessments

Local laboratories will perform all clinical laboratory tests using standard procedures, and results will be provided to the Investigator. Abnormalities in clinical laboratory tests that lead to a change in subject management (e.g., dose modification, requirement for additional medication, treatment or monitoring) are considered clinically significant for the purposes of this study, and will be recorded on the case report form (CRF). If laboratory values constitute part of an event that meets criteria defining it as serious, the event (and associated laboratory values) must be reported as a serious adverse event (SAE).

Refer to [Appendix E](#) for details of laboratory tests for this study. In addition, blood tumor markers (if clinically indicated) such as CEA and/or CA19-9, will be obtained at baseline and at every restaging.

5.5 Adverse Event Assessment

AE definition is described in [Section 10.1](#). AEs will be documented throughout the study. AE seriousness, grade, and relationship to study drug will be assessed by the Investigator using NCI-CTCAE version 4.0 (http://evs.nci.nih.gov/ftp1/CTCAE/CTCAE_4.03_2010-06-14_QuickReference_5x7.pdf).

SAE definitions and reporting requirements are described in [Section 10.2](#).

Select non-serious and serious adverse events also known as Events of Clinical Interest (ECI) must be recorded and reported as described in [Section 10.3](#).

5.6 Tumor Assessments

Tumor response will be assessed using RECIST version 1.1 and irRC. Radiographic imaging will be performed with CT scan of chest/abdomen/pelvis with and without contrast and/or MRI scan of abdomen/pelvis every 3 cycles (i.e., every 9 weeks) after the start of study treatment. The same method for tumor assessment should be employed at every assessment.

5.6.1 RECIST version 1.1

RECIST is a set of published rules that define when cancer patients improve ("respond"), stay the same ("stabilize"), or worsen ("progression") during treatments. The original criteria were published in February 2000 by an international collaboration including the European Organization for Research and Treatment of Cancer (EORTC), National Cancer Institute (NCI) of the United States and the National

Cancer Institute of Canada Clinical Trials Group. RECIST 1.1, published in January 2009, is an update to the original criteria and will be used for this study.

Refer to [Appendix A](#) for definition of target lesions, methods of measurement and all other related criteria for RECIST version 1.1. The following summarizes the definitions of the criteria used to determine objective tumor response for target lesions:

- **Complete Response (CR):** Disappearance of all target lesions. Any pathological lymph nodes (whether target or non-target) must have reduction in short axis to <10 mm.
- **Partial Response (PR):** At least a 30% decrease in the sum of diameters of target lesions, taking as reference the baseline sum diameters.
- **Progressive Disease (PD):** At least a 20% increase in the sum of diameters of target lesions, taking as reference the smallest sum on study (this includes the baseline sum if that is the smallest on study). In addition to the relative increase of 20%, the sum must also demonstrate an absolute increase of at least 5 mm. (Note: the appearance of one or more new lesions is also considered progression).
- **Stable Disease (SD):** Neither sufficient shrinkage to qualify for PR nor sufficient increase to qualify for PD, taking as reference the smallest sum diameters while on study.

5.6.2 Immune-Related Response Criteria

The responses that are seen with immunotherapeutic agents may extend beyond those of cytotoxic agents and could include responses after disease progression that is not captured by RECIST. To account for this, for this study, immune-related response criteria (irRC) will be used to allow for more comprehensive evaluation of clinical activity. Conventional response criteria may not adequately assess the activity of immunotherapeutic agents because PD (progressive disease) by initial radiographic evaluation does not necessarily reflect therapeutic failure, thus stopping the study treatment with initial perceived PD may be premature.

Refer to [Appendix B](#) for definitions and guidelines of the irRC. The overall response according to the irRC is derived from time-point response assessments (based on tumor burden) as follows:

- **irCR:** complete disappearance of all lesions (whether measurable or not, and no new lesions) confirmation by a repeat, consecutive assessment no less than 4 weeks from the date first documented
- **irPR:** decrease in tumor burden $\geq 50\%$ relative to baseline confirmed by a consecutive assessment at least 4 weeks after first documentation
- **irSD:** not meeting criteria for irCR or irPR, in absence of irPD
- **irPD:** increase in tumor burden $\geq 25\%$ relative to nadir (minimum recorded tumor burden) confirmation by a repeat, consecutive assessment no less than 4 weeks from the date first documented

